Absorbed blood in gauze: measure weight of the gauze before the operation then calculate the difference after the operation.

Absorbed amount of blood using inhalator: blood collected in the inhalator bottle will be moved to the 50cc syringe then the amount of blood will be measured. If saline is used for wash out operation region during the operation, that amount will be omitted.

- ② Operation time
- ③ Transfusion volume

(2) Pre- and Post- operation management

- i. Within a month from the date of operation: A laboratory test (CBC, admission panel, CRP, triglyceride, amylase, PT, aPTT), age, medical history, ASA classification, weight, height.
- ii. 1 day before operation: bowel preparation (empty stomach and enema): use of a laxative before operation (Mg. citrate powder intake, suppository bisacodyl 10mg) and suppository glycerin enema and bisacodyl 10mg on the day of operation.
- iii. low molecular weight heparin (LMWH): to prevent DVT, hypodermic medication of 20mg 1 time/ 1day may possible after 2 ~3 days post operatively.

(3) Post-operative evaluation

- PCA (patient controlled analgesia): includes Morphin and fentanyl. When need additional pain control, Nalbuphin (IM) or Fentanyl patch will be used
- 2 From POD 1 to 4, VAS pain score will be measured daily.
- 3 Gas out, day of starting liquid diet will be recorded
- ④ Complications: Within the follow-up period, from the end of operation to 2-3 weeks after discharge, patients will be monitored to check for complications and mortality before POD 30. Complications will be measured by Clavien-Dindo classification. Any reasons for re-admission through an out-patient clinic or emergency during the followup period will separately be recorded.

(4) Laboratory test

i. POD 2, 4: Blood test (CBC, admission panel, CRP, triglyceride, amylase)

ii. POD 2: Amylase and triglyceride test in the drain. Measurement of drainage by 1-3 days after surgery

iii. Cytokines Test:

- Serum IL-6, IL-10: Obtain peripheral blood in 5ml bottle of EDTA bottle : just after the induction of the anesthetia, 2-3 hours after the end of the operation, the 2nd post-operative day, and the 4th post-operative day.
- EDTA bottle is centrifuged at 3000 rpm for 15 minutes as soon as possible after collection. It is divided into 200ul each, and then cytokine assay is asked to clinical research laboratory. On holidays when it is difficult to conduct the test, it is centrifuged, stored at -80 °C and analyzed at the day available.

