- After the screening number was assigned, the subjects who satisfied all the inclusion criteria and were not eligible for any exclusion criterion were judged to be suitable for the study. After the insertion of the laparoscopic trocar under general anesthesia, (Eg, after a confirmation of unexpected intraperitoneal or severe adherence do not exist), randomization should be performed. A randomization number (patient ID) will be awarded in a strictly sequential manner in accordance with the randomization table generated by the medical statisticians in advance.
- The randomized method uses a centralized stratified block randomization method to ensure a balanced distribution among the three groups. Institutes and the presence of incision during anastomosis (intracorporeal or extracorporeal anastomosis) will be the stratification factors.
- If a clinical trial subject discontinues clinical trials, the random assignment number assigned to the subject will not be re-used and the subject will not be able to participate in the trial again.
- The trial will be conducted with a single blind spot. Therefore, the practitioner knows the contents of the randomization, but does not disclose the contents of the clinical trial subjects for about 4 weeks after the end of the clinical study.

3) How to use test medical device, combination therapy, reasons for selection when using treatments

Energy-based devices are used in accordance with the manufacturer's manual and the commonly used principles of laparoscopic surgery, and the sites of use during surgery are as described in above 9-1)-(2).

4) Observation items, clinical examination items and observational examination methods

- (1) Primary endpoint: Serum C-reactive protein (CRP) at POD 2
- (2) Secondary endpoint:
 - Blood loss during operation, amount of blood transfusion

- IL-6, IL-10 in serum and ascites at 2-3 hours after surgery and POD 2, 4
- Complication within 30 days after surgery, mortality rate
- At 4 days postoperatively, serum CRP
- Postoperative visual pain score (VAS score)
- The timing of gas release after surgery, start time of liquid diet
- Length of stay, re-admission, emergency room visit and reasons
- Amount of drainage after surgery
- Concentration of triglyceride and amylase in drain
- Amount of Indocyanine green in the peritoneal cavity after surgery, which is injected submucosally before dissection (only in Seoul National University Hospital)
- Number of resected lymph nodes

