- 16) Endocrine: Diabetic ketoacidosis, hyperglycemic hyperosmolar state, Addison's disease, hypothyroidism, etc. Clinically diagnosed
- 17) Stasis: Refers to the case where food is obstructed to pass through the anastomosis, even though there is no evidence of intestinal obstruction, stenosis, leakage, or peritonitis.

- 18) Pancreatic leakage: A case when the amylase level of the drain tube 3 days or more after surgery exceeds 540 U/L, which is three times the normal maximum value of 180 U/L of the normal blood test (1, 3, Check on day 5).
- 19) Chylous ascites: Suspected when the color of a clear white fluid is found with the naked eye, and JP diagnoses that triglyceride is 110 mg/dL.
- 20) Deep Vein Thrombosis
- 21) Central venous infections

9) Evaluation standards, evaluation methods and analysis methods (statistical analysis methods, etc.)

- (1) Primary endpoint: Two days after surgery, serum CRP
- ; Student's t test or ANOVA test was performed by using the mean of CRP value on the second day between the three groups.
- (2) Secondary endpoint:
- Blood loss during operation (ml), amount of blood transfusion (pint); Output-input (ml). Gauze measures the total weight of gauze used during surgery and calculates the difference from the gauze weight measured before surgery. Inhalation volume is calculated by subtracting the amount of 0.9% physiological saline solution applied to the surgical site from the total inhalation volume.
- Serum IL-6, IL-10

Serum IL-6 and IL-10 levels were measured at baseline immediately after general anesthesia and insertion of the trocar. The mean value of serum IL-6 and IL-10 levels 2-3 hours after the operation, the 2nd postoperative day, and the 4th postoperative day are compared by Student's t test or ANOVA test.

- Amount of remaining ICG: Total amount of the remaining ICG will be calculated by the mean value of concentration of the ICG measuring 3 sets for each patient multiplied by 500 (ml) (600 or 700 ml for corresponding cases), and the mean value of the amount of ICG will be compared between each group using t test.

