- Complications and mortality rate within 30 days after surgery: Clavien-Dindo classification is used to grade the complications of the three groups and the $\chi 2$ test is performed using the Cross Table for the frequency of complications and Grade IIIa complications. For the total complications, the Student's t test or the ANOVA test was performed using the Comprehensive Comorbidity Index between the three groups.

- After 4 days postoperatively, serum CRP, amylase, serum/ascites triglyceride: The preoperative mean value was used as the baseline and the Student's t test or the ANOVA test was performed on the mean value of the three groups at the 4th postoperative day
- Post-operative pain medication frequency: Student's t test or ANOVA test is performed on the average daily frequency of use among the three groups of non-PCA narcotic analgesics.
- Postoperative visual pain score (VAS score): The mean postoperative VAS score between the three groups is verified by Student's t test or ANOVA test.
- Post-operative transfusion, gas evacuation, liquid diet initiation: If the postoperative Hb < 8, transfusion can be performed under the judgment of the tester and record transfusion. The mean number of days from the day of surgery was verified by Student's t test or ANOVA test among the three groups.
- Length of hospital stay: The average number of days between surgery and discharge is assessed by Student's t test or ANOVA test among the three groups.
- Re-admission, emergency room visit: Within 30 days from the date of surgery, record admission / visit and evaluate complications if you are re-admitted to the hospital or visited the emergency room.
- A new version of the harmonic scalpel was introduced during the research and the target of the ultrasonic group is being studied with a new product. (Since IRB approval in July 2018)
- We will compare the results of the patients who underwent surgery in the ultrasonic group regarding to old instrument versus new instrument. In the comparison between the groups, it will be analyzed whether there is a difference between the inclusion and the non-inclusion of the subject who underwent surgery with the old apparatus. In these ways, it will be notated in the final report whether there is any influence on the results of the study by the change of the device.

9-1) General principles of statistical analysis.

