A multivariable analysis of primary and primary secondary efficacy variables is performed. Multivariate analysis uses multiple linear regression models or multiple logistic regression models depending on the type of outcome variable. The main independent variable is the test, we will include the gender and stage of the stratified variables used in randomization in the model and the perturbed variables identified in the demographic and clinical history data analyzes to control the effect. For repeated measurement data, perform a multivariate analysis using the generalized estimation equation (GEE). If a significant interaction effect is found between the treatment group and the participating laboratories and / or the treatment group and the confounding variables, the effect is controlled by including the interaction term in the multivariate model.

• The content of the pre-planned subgroup analysis to be performed in this trial is as follows:

- Gender Male Female)
- BMI (<25 / ≥25)
- Cancer stage (TNM stage)
- Operator
- In vitro / Internal Anastomosis
- The differences between the groups were assessed using the Student's t-test (or the corresponding nonparametric Wilcoxon rank-sum test) or the χ2 test (or Fisher's exact test, the corresponding nonparametric method) Analysis. If control of disturbance variables is required, multivariate analysis is performed.

9-2) Treatment of missing values.

In general, the missing value will be treated as a missing state, and no alternative missing statistic is used. Therefore, only observations will be used for data analysis. Discrepancies data are replaced by missing values at the responsibility of the clinical trial manager.

10) Clinical trial and treatment standard

The same type of treatment and treatment will be given to patients with general gastric cancer who are being treated at Seoul National University Hospital.

11) Study Schedule

- 42 months after IRB approval: registration of clinical trial subjects and clinical trials
- 42 months ~ 48 months: Data analysis and presentation

12. Data and Safety Monitoring Plan

1) The person in charge of monitoring

- * Monitoring supervisor: [name], Associate Professor, Surgery, Seoul National University Hospital
- * Person in charge of monitoring: [name], Department of Nurse, Seoul National University Hospital

2) Data and safety information monitoring items

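### The stated test for post-operative serum IL-6 and IL-10 leaves out the scheduled pre-dissection baseline, and the planned GEE does not say how that baseline enters: a valid analysis, but possibly less efficient than it could be.

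*Combined protocol and SAP*

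**What the plan says.** All references are to the protocol.

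- **Sampling.** Section 11, 1)(4) sets four serum cytokine samples: "just after the induction of the anesthetia, 2-3 hours after the end of the operation, the 2nd post-operative day, and the 4th post-operative day". Neither that section nor the schedule table limits them to one hospital; only the ICG work is limited in that way.
- **Baseline and stated test.** Section 11, 9)(2): "Serum IL-6 and IL-10 levels were measured at baseline immediately after general anesthesia and insertion of the trocar". The next sentence takes the three post-operative times and ends "the 4th postoperative day are compared by Student's t test or ANOVA test". No covariate is named.
- **Rank.** Section 11, 4)(2) lists these among the secondary endpoints: "IL-6, IL-10 in serum and ascites at 2-3 hours after surgery and POD 2, 4". The point here concerns serum only, because the baseline described is a serum sample.
- **Adjusted analyses elsewhere.** Section 9-1: "A multivariable analysis of primary and primary secondary efficacy variables is performed". On covariates: "we will include the gender and stage of the stratified variables used in randomization in the model and the perturbed variables identified". On serial data: "For repeated measurement data, perform a multivariate analysis using the generalized estimation equation (GEE". None of these sentences mentions the baseline value of the outcome.
- **A neighbouring endpoint.** For day-4 CRP, amylase and triglyceride, section 9)(2) says "The preoperative mean value was used as the baseline", but the test is again on day-4 means.
- **Still to come.** Section 9-1 leaves a separate SAP to be written before the database is locked.

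**The concern.** Randomisation follows trocar insertion (section 11, 2)), and the baseline cytokine sample is drawn at induction or just after the trocars go in. The two sections differ slightly on the moment, but both put it before dissection. The assigned device cannot have affected the value, so it is a legitimate covariate and it will already be in the database.

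Where the baseline predicts the post-operative value, a t test or ANOVA on post-operative means leaves that variation in the error term. The intervals are then wider than they need be, and the estimate moves more with chance differences between arms at baseline.

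There is also a question of prespecification. The text permits at least four analyses: post-operative means, change from baseline, GEE with baseline as one of the outcome times, or a baseline-adjusted model. They can give different answers, and nothing says which one leads. IL-6 and IL-10 come first among the secondary efficacy indices in the study summary and bear on the inflammation question, so the choice should be fixed in advance.

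**Working it through.** **1. The plan's own figure.** Section 10, 3) uses CRP means of 11.5 and 8.0 (difference 3.5), SD 6.6 in both groups, two-sided alpha 0.05 and 80% power.

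- Normal approximation: n = 2 × (1.960 + 0.842)² × (6.6/3.5)² = 55.8, so 56 per group.
- Two-sample t test (noncentral t): 56.8, so 57 per group, as stated. Power at 57 is 80.1%.
- Dropout: 57/0.9 = 63.3 per group, or 190 over three groups. The stated 189 is 3 × 63, which is close enough.

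This figure belongs to day-2 CRP. No SD, effect or power is stated for IL-6 or IL-10. I use 57 below only as a convenient number of evaluable patients per group.

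**2. Effect of adjusting for baseline.** Let r be the within-group correlation between the baseline and a post-operative value on the analysis scale. The documents give no r, so a range is assumed. For a linear model:

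- variance factor = 1 − r²
- equivalent unadjusted n = 57/(1 − r²)
- power is for an effect of 0.53 SD, which has 80% power unadjusted at 57 per group, with the SD multiplied by √(1 − r²)

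| r (assumed) | Variance factor | Variance reduction | 57 per group is worth | Power from 80% |
|---|---|---|---|---|
| 0 | 1.00 | 0% | 57.0 | 80.0% |
| 0.1 | 0.99 | 1% | 57.6 | 80.4% |
| 0.2 | 0.96 | 4% | 59.4 | 81.6% |
| 0.3 | 0.91 | 9% | 62.6 | 83.6% |
| 0.4 | 0.84 | 16% | 67.9 | 86.4% |
| 0.5 | 0.75 | 25% | 76.0 | 89.9% |
| 0.6 | 0.64 | 36% | 89.1 | 93.8% |

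The equivalent-n column only restates 1/(1 − r²) on a base borrowed from CRP. It is not a statement about the trial's power for cytokines.

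**3. Why the role of baseline matters.** With equal SDs before and after surgery, a change score has variance factor 2 − 2r. At r = 0.3 that is 1.40, against 1.00 unadjusted and 0.91 with ANCOVA. It is worse than the unadjusted test whenever r < 0.5. It never beats ANCOVA, because (2 − 2r) − (1 − r²) = (1 − r)² ≥ 0. A GEE that treats baseline as an outcome time, and reads the effect from an unconstrained group-by-time term, is in essence a comparison of changes. The GEE sentence therefore does not by itself secure the gain in the table.

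**4. Covariates that are named.** Section 9-1 calls gender and stage the stratification variables. Section 11, 1) and 2) name institute and intracorporeal or extracorporeal anastomosis. As written, the adjusted model would not reliably contain the factors used to randomise.

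**The case against.** The strongest reply is that the plan does more than the t test. Four serial cytokine samples are repeated measurements, so the GEE sentence reaches them, and the multivariable models may do so too. The detail can properly wait for the SAP. The unadjusted comparison is a sound randomised analysis in any case. The gain could be negligible: the baseline precedes the surgical stimulus, the outcome is the response to that stimulus, and entry requires pre-operative CRP of at most 1.0 mg/dl, which may narrow the spread of baseline inflammation. Section 9-1 also allows a rank test when parametric assumptions fail, and the 1 − r² formula does not describe that test.

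Most of this stands, and it rules out several stronger readings that a reader might infer:

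- **That the baseline is never used.** The GEE or multivariable model could include it. The text is silent on this, and silence does not show that it is left out.
- **That chance imbalance biases the comparison.** The standard error of the unadjusted test already allows for it.
- **That a material amount of precision is certainly lost.** No r is given, and nothing in the documents supports r of 0.3 or more.
- **That the trial's main conclusion is at risk.** Section 8, 2) ties the hypothesis to day-2 CRP, and section 11, 4)(2) lists blood loss and transfusion ahead of the cytokines.

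The reply does not remove the gap. The only test attached to these endpoints is unadjusted, the set of variables due for multivariable analysis is not defined, and no section names baseline IL-6 or IL-10 as a covariate.

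**Conclusion.** The point holds as a matter of efficiency and prespecification on a secondary endpoint. The stated test ignores a baseline that is scheduled for every patient, and the planned adjusted models leave its role open. I am confident about that gap but not about the size of the loss. On a linear scale the variance reduction is r², from 0% to 36% over the assumed range of r = 0 to 0.6, and the lower part of that range is plausible. Validity, the primary CRP analysis and the sample size are not affected. The change is worth making because it costs almost nothing even if r turns out to be small.

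**What to change.** In the SAP, before database lock:

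1. Name one main analysis for each post-operative serum IL-6 and IL-10 value: an ANCOVA at each time, or the planned GEE over the three post-operative times. In either case, enter the patient's own baseline as a covariate and not as an outcome time point. Keep the t test or ANOVA as a supporting analysis.
2. Prespecify the scale, for example log outcome with log baseline, so that the choice between a parametric and a rank test is not left to the data.
3. Adjust for the factors actually used to randomise, institute and anastomosis type, and reconcile section 9-1's gender and stage with them.
4. State how a missing baseline is handled. Under section 9-2's observed-data rule, such a patient would otherwise drop out of the adjusted model.
5. Clarify in the same way what role the baseline plays for day-4 CRP, amylase and triglyceride.

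The cost is SAP wording, about one degree of freedom for the baseline term and a few for the strata. No extra samples are needed. If r is near zero, there is simply no gain.

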Comparison of perioperative outcomes between bipolar sealing device and ultrasonic shears during laparoscopic gastrectomy for early gastric cancer

Version No: 2.1

Date: 2021.7.1

Study Institution: Seoul National University General Surgery
Study in charge: [name]

Study Summary

Study title	(Korean) 위암 환자의 복강경 위절제술에서 에너지 기반 절단기구 간
	의 비교 연구
	(English) Comparison of perioperative outcomes between bipolar
	sealing device and ultrasonic shears during laparoscopic
	gastrectomy for early gastric cancer
Study in charge	[name], associate professor, Seoul National University
	Hospital
Fund support	Medtronic, Inc

	The purpose of this study was to compare the perioperative outcomes								
Study purpose	for patients including inflammatory response of energy-based shears								
	devices used in laparoscopic gastrectomy for early gastric cancer.								
Study design	A randomized comparison between three groups by single blind								
Study design	method.								
Study period	RB approval date ~ 4 years								
Study Subject	Preoperative gastric cancer in the middle or lower part of stomach,								
(Clinical trial	which is expected to be 1 stage.								
drug etc)									
Number of	189 people (3 groups x 63 people)								
subjects									
Vulnerable subjects	No applicable								
	Three energy-based devices were randomly assigned to the group of								
	patients with early gastric cancer in the lower or middle part of								
	stomach, followed by laparoscopic distal gastrectomy by single blind								
	method.								
Study Method	Main analysis group								
	Group A: Ultrasonic shears								
	Group B: Bipolar electrocautery								
	Explorative analysis group								
	Group C: Hybrid devices								
	Primary evaluation index: Serum CRP after 2 days of post-operation								
Validity	Secondary evaluation index: Serum IL-6, IL-10, Amount of								
evaluation	Indocyanine green in the peritoneal cavity after surgery, which is								
	injected submucosally before dissection								

	Second Evaluation Index:						
Safety evaluation	1. Blood loss during surgery						
	2. Complications within 30 days after surgery						
	The purpose of this study was to investigate the perioperative						
Possible effects and outcomes	outcomes of different types of energy-based devices which are						
	considered as the most important factor for laparoscopic gastric						
	cancer and to provide scientific basis for selecting safe and effective						

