- (3) Patients who should undergo other long-term merger resection during distal gastrectomy. (except cholecystectomy)
- (4) Patients with significant ascites by CT.
- (5) Patients with cirrhosis in CT brfore surgery
- (6) Patients with heart disease (history of uncontrolled hypertension, angina or coronary artery disease, history of cardiac muscle disease, Ejection Fraction <50%)
- (7) Patients with inappropriate renal function (serum creatinine > 1.4 mg/dL or BUN > 26 mg/dL)
- (8) Patients with abnormal coagulation (PT INR > 1.2 or aPTT > 45 sec)
- (9) Uncontrolled diabetic patients
- (10) Inflammatory bowel disease patients including Crohn's disease, ulcerative colitis, tuberculous enteritis
- (11) Patients taking aspirin or platelet inhibitors within 5 days before surgery
- (12) Patients taking anticoagulants

- (13) Patients with the history of steroid use which needs stress dose inoculation
- (14) Pregnancy
- (15) Other patients who are deemed unable to participate in the clinical trial by the tester
- (16) History of sensitivity to iodine, in case the test using indocyanine green is applied
- (17) Previous history of gout

3) Target number of subjects and basis of calculation

Total target number: 189, competitive enrollment at SNUH and SNUBH Calculation methods of the subjects

Primary evaluation variable: Cerum CRP value on Post-op 2nd day **Subjects of the study**

Main analysis group

- A. Ultrasonic shears
- B. Bipolar sealing device

Explorative analysis group

C. Hybride device

Study hypothesis:

- Null hypothesis: No difference in CRP value on post-op 2nd day between two groups.
- Alternative hypothesis: Difference in CRP value on post-op 2nd day between two groups.

Hypothesis for calculation of number of subjects:

- (1) Level of significance, $\alpha = 0.05$
- (2) Ratio between groups, group A: group B = 1:1
- (3) Type 2 error (β) is 0.20, retaining power of the test at 80%
- (4) Ultrasound dissector and Bipolar's post-op's CRP average and standard deviation was 11.5 ± 6.6 and 8.0 ± 2.8 from preceding research of "Research of availability and safety in using Articulating bipolar vessel sealer system in early Robotic gastrectomy in early stage gastric cancer". Subjected patients were 17, small in numbers and it was for Robotic LAP surgery, not conventional LAP surgery. Therefore, to avoid chances for reflecting not enough subjected patients, we have calculated subjected patient numbers from conservative standard deviation.

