A Statistical Analysis Plan (SAP) will be created before the database locks. A blinding review of the data will focus primarily on issues related to the exclusion of patient or patient data from missing and analyzed data.

The subjects to be validated for the data obtained from the subjects of the clinical trial are

classified into the ITT (intention-to-treat) analysis group and the PP (per protocol) analysis target group.

- ITT analysis group consisted of all randomized subjects after satisfying the selection / exclusion criteria.
- The subjects who underwent the PP analysis were those who completed the clinical trials of the ITT target group, and observed the primary efficacy variables as planned without violating the critical clinical trial plan. Completion of the clinical trial is defined as discharge following normal procedure without further hospitalization after surgery. Critical clinical trial protocol violations include:
 - · Violation of selection / exclusion criteria
 - · Random assignment violations
 - Take medication for concomitant medication
 - In case of any other serious clinical trial protocol violation
- The analysis of the basic characteristics of the patients, including demographic data and clinical history data, is evaluated using the ITT analysis group. All of the validation variables were analyzed for the ITT group and the PP group. The results of the study on serum CRP at day 2 postoperatively were used as the main evaluation group.

Safe Safety evaluation variables such as adverse events and adverse reactions are analyzed using the safety analysis target group.

- The safety analysis group consisted of all subjects who underwent randomized placement.
- Statistical tests for all efficacy / safety parameters should be performed at the 5% significance level. If the data do not meet the assumptions needed to perform a parametric test, a non-parametric test such as the Wilcoson rank-sum test is performed.

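### Every efficacy and safety parameter gets its own 5% test and secondary results are not labelled exploratory, leaving a roughly 35–68% chance of at least one false A vs B difference among them

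*Combined protocol and SAP*

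**What the plan says.** The testing rule is in section 11, item 9-1): "Statistical tests for all efficacy / safety parameters should be performed at the 5% significance level". The same item adds: "All of the validation variables were analyzed for the ITT group and the PP group".

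The confirmatory question is narrow. Section 11, item 4) gives "Primary endpoint: Serum C-reactive protein (CRP) at POD 2", and section 10-3) states one hypothesis pair: "Alternative hypothesis: Difference in CRP value on post-op 2nd day between two groups". The two groups are A and B. Group C is called explorative in the Study Summary and in section 10-3).

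The secondary list is long. In the Study Summary the line starts "Secondary evaluation index: Serum IL-6, IL-10, Amount of" and goes on to indocyanine green (ICG); blood loss and 30-day complications appear there as safety items. Section 11, items 4) and 9), add many more, mostly with a t test or ANOVA. For ICG the wording is "the mean value of the amount of ICG will be compared between each group using t test".

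Item 9-1) also plans GEE for repeated measurements, refers to leading secondary efficacy variables without naming them, and promises a SAP before database lock. No hierarchy, alpha split or multiplicity correction appears anywhere, and nothing says that the secondary results are exploratory.

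**The concern.** The trial is meant to inform the choice of device, and its size is justified for day 2 CRP only. If CRP shows no difference, the rule in 9-1) still allows any secondary result with p<0.05 to be reported as a significant device difference, on the same terms as the primary. With a list this long, such a result has a substantial probability by chance alone. The funder is also the listed manufacturer of the bipolar device, so a secondary claim made without a pre-stated rule would be easy to challenge.

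**Working it through.** **The plan's own figure.** The pilot data are given as "CRP average and standard deviation was 11.5 ± 6.6 and 8.0 ± 2.8 from preceding research"; the sample size table uses SD 6.6 in both groups, α = 0.05 and 80% power.
- Normal approximation: n = 2 × (1.960 + 0.842)² × (6.6/3.5)² = 55.8, so 56 per group. The noncentral t calculation gives 57 (power 80.1%), as stated.
- A one-sided test would need only 44, so the design is two-sided, in line with the non-directional alternative.
- 57/0.9 × 3 = 190, against 189 stated (63 × 3), a rounding difference.

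This covers one endpoint and one contrast.

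**Counting secondary tests per contrast, from section 11, item 9).**

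| Item | Tests |
|---|---|
| Blood loss, transfusion amount | 2 |
| IL-6 and IL-10, three times each | 6 |
| ICG | 1 |
| Complication frequency, Grade IIIa | 2 |
| Overall complication index | 1 |
| Day 4 CRP, amylase, serum and ascites triglyceride | 4 |
| Analgesic frequency | 1 |
| VAS pain | 1 |
| Post-operative transfusion, gas, liquid diet | 3 |
| Length of stay | 1 |
| **Total** | **22** |

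A smaller count is defensible. Setting aside blood loss and the three complication measures as safety leaves 22 − 4 = 18. One GEE test per cytokine instead of three leaves 18 − 4 = 14.

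**Chance of at least one false positive, no true differences, A vs B only.**
- Independent tests: 1 − 0.95^m. For m = 22 this is 1 − 0.95^22 = 67.6%, with 22 × 0.05 = 1.1 false positives expected.
- Equally correlated two-sided normal tests, by numerical integration over a shared factor. The documents give no correlations, so these are assumptions.

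| Tests | ρ = 0 | ρ = 0.3 | ρ = 0.5 |
|---|---|---|---|
| 22 | 67.6% | 56.9% | 43.9% |
| 18 | 60.3% | 50.9% | 39.8% |
| 14 | 51.2% | 43.8% | 34.8% |

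For 22 tests the 50% line is crossed at ρ of about 0.41.

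**Sensitivity, 22 tests.**
- Five clinical clusters instead of a uniform correlation: 56% with 0.5 within and 0.2 between clusters; 49.7% with 0.7 and 0.2.
- One three-group ANOVA per endpoint instead of A vs B: 67.6%, 57.4% and 44.4% at ρ = 0, 0.3 and 0.5, almost unchanged.
- A false result favouring one named device: 1 − 0.975^22 = 43% if independent.

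**The case against.** The strongest reply is that the plan already limits its confirmatory claim: one hypothesis pair, one primary endpoint, A vs B named as the main concern, everything else called secondary, and C called explorative. Unadjusted secondary tests are common, and a SAP is still to come. Much of this stands. The secondary count does not change the error rate of the A vs B test on day 2 CRP, and the comparisons with C already carry the right label. But calling an endpoint secondary is not the same as calling it exploratory. Item 9-1) sets a significance test for each parameter, and nothing commits the later SAP to any control.

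The count is also open to challenge. Item 9) gives measurement instructions but no named test for blood loss and intra-operative transfusion, GEE could reduce the cytokine tests, and safety tests should not be in a figure used to argue for restraint on efficacy claims. These objections are sound, and the lower end of the range reflects the last two. In the other direction, the 22 leave out drain volume, node count, separate mortality and daily VAS tests, per-protocol repeats and subgroups.

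A reader might infer two stronger things. The first is that a false positive is more likely than not whenever the tests are no more than moderately correlated. At a uniform 0.5 the figure is 44% even with 22 tests, so this is not supported. The second is that all three pairwise contrasts will be tested on every endpoint, which would give about 94%, 88% and 75% at correlations 0, 0.3 and 0.5. Wording that suggests pairwise testing is used only for ICG, most other items allow a single three-group ANOVA, and two of the three contrasts involve the explorative arm.

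**Conclusion.** The concern holds as a gap in how secondary results may be interpreted. If no secondary endpoint truly differs, the plan as written carries roughly a 35–68% chance of at least one false significant A vs B difference. The range depends on the count (14 to 22) and on the assumed correlation (0 to 0.5). For 22 tests the chance passes one half only if the average correlation is below about 0.4; for 14 tests it is barely one half even under independence (51%). If some secondary endpoints do differ, fewer true nulls remain and the chance is lower.

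**What to change.** Replace the sentence in 9-1), or put the following in the SAP before database lock:

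*The only confirmatory test is A vs B on POD 2 serum CRP, two-sided 5%. All other efficacy comparisons, and all comparisons involving group C, are reported as differences with 95% CIs, are labelled exploratory, and cannot on their own support a claim of device superiority. Safety comparisons are reported as differences with 95% CIs without multiplicity adjustment.*

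Leaving safety unadjusted avoids suppressing a harm signal. The text should also list which endpoints count as safety, because the Study Summary puts blood loss and complications there while section 11, item 4) lists them among the secondary endpoints.

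A Holm procedure for IL-6, IL-10 and ICG, opened only if the primary test is significant, is optional. If used, it needs one named summary per endpoint and a note that ICG is measured at one site only, so on fewer patients.

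The change is one paragraph, needs no new patients or data, and costs the primary test no power. The price is that fewer secondary results can be called significant.
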